6.3.2.1.3 Guidelines for the treatment of alpelisib induced hyperglycemia

Alpelisib, like other PI3K inhibitors, may affect glucose homeostasis which could result in increases of plasma glucose and insulin resistance (Busaidy 2012). Alpelisib induced hyperglycemia is generally manageable with adequate antidiabetic treatment. Alpelisib induced hyperglycemia typically occurs within the first month of treatment. Patients with pre-diabetes (i.e. FPG 100 – 125 mg/dl; 5.6 - 6.9 mmol/L) and those with an established diagnosis of type 2 diabetes mellitus should be monitored carefully, thus allowing an early detection and prompt management of increases in FPG while on alpelisib/placebo treatment. However all patients, even those with FPG within normal limits at screening, may develop alpelisib induced hyperglycemia. Patients should always be instructed to follow dietary guidelines provided by the American Diabetes Association, e.g. small frequent meals, low carbohydrate content, high fiber, balancing carbohydrates over the course of the day; three small meals and 2 small snacks rather than one large meal and exercise, as appropriate.

Detailed guidelines for management of alpelisib induced hyperglycemia is provided in [Table 6-3](#) following discussion with an advisory board. This includes early administration of metformin. Metformin may be titrated to a daily dose of 1000 mg BID. Local protocols per standard clinical practice may be followed for monitoring and managing hyperglycemia. Fasting plasma glucose may be performed both locally and/or centrally for rapid availability for safety evaluation and management guidance. Special attention should be paid to the risk of hypoglycemia in patients interrupting alpelisib treatment and concomitantly receiving insulin and/or sulfonylureas. Due to the short half-life of alpelisib, all glucose lowering medications should be discontinued when alpelisib is stopped.

Consultation with a diabetologist is highly recommended for better assessment and management of alpelisib-induced hyperglycemia.

6.3.2.1.4 .Follow-up on amylase or lipase elevation (\geq CTCAE Grade 3)

Patient with amylase or lipase elevation \geq CTCAE Grade 3 must be tested weekly (or more frequently if clinically indicated) until \leq Grade 1 (or baseline). After resumption of dosing, continue to test weekly for one additional cycle. If no reoccurrence of \geq Grade 2 event, continue monitoring every cycle.

An exception to these follow-up guidelines will be made for cases of isolated amylase elevations in which amylase fractionation demonstrates that pancreatic amylase is \leq Grade 1. In such cases, total amylase and fractionated amylase should be monitored weekly (or more frequently if clinically indicated) for 4 weeks. If pancreatic amylase remains \leq Grade 1, subsequent monitoring must be performed at least every 4 weeks (or more frequently if clinically indicated).

Patients who discontinue study treatment due to pancreatic toxicity must be monitored weekly (or more frequently if clinically indicated) until the event resolves to \leq grade 1 or stabilization occurs (no CTCAE grade change over 4 weeks).

If amylase and/or lipase elevations are accompanied by new or progressive unexplained abdominal symptoms such as severe pain or vomiting, withhold study treatment, then perform diagnostic procedures (e.g. abdominal CT scan or ultrasound) to exclude pancreatic pathology.

See also dose modification guidelines described in [Table 6-3](#).

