- Section 6.3.2.1.1: Management of Pneumonitis/ILD: included ILD as a selected toxicity
- Section 6.3.2.1.2: Guidelines for the treatment of study drug induced skin toxicity: included DRESS as a skin toxicity and guidelines for follow up on skin toxicity further clarified
- Section 6.3.2.1.3: Guidelines for the treatment of alpelisib induced hyperglycemia: Update on guidance for glucose lowering medications after discontinuation of alpelisib
- Section 6.3.2.1.5: Follow up on potential drug-induced liver injury (DILI) cases: Additional information on the diagnosis of DILI and clarification on the approach if DILI is confirmed or unlikely
 - Table 6-4: Alternative causes of liver disease: Table added
- Section 6.3.2.1.6: Guidelines for hypersensitivity: Section added
- [REDACTED]
- [REDACTED]
- [REDACTED]
- Section 6.5.3: Treatment blinding: Timing of unblinding clarified
- Section 7.1: Study flow and visit schedule: Frequency of assessments reduced for patients in longer-term efficacy follow-up
 - Table 7-1: Visit evaluation schedule: Efficacy assessment schedule updated
- Section 7.1.6: Efficacy follow-up Frequency of assessments changed for patients in longer-term efficacy follow-up
- Section 7.2.1: Efficacy assessment Frequency of assessments changed for patients in longer-term efficacy follow-up
 - Table 7-2: Imaging assessment collection plan Frequency of imaging assessments changed for patients in longer-term efficacy follow-up
- Section 7.2.2.7.1: Electrocardiogram (ECG)
 - Table 7-5: Local ECG collection plan
- Section 7.2.2.7.2: Cardiac imaging – MUGA scan or ECHO
- Section 7.2.6: Patient reported outcomes Frequency of PROs changed for patients in longer-term efficacy follow-up
- Table 7-10: Patient reported outcomes collection plan
- Section 14: Appendix 7: Liver event and Laboratory trigger Definitions and Follow-up Requirements Section/Table added

IRBs/IECs

A copy of this amended protocol will be sent to the Institutional Review Board (IRBs)/Independent Ethics Committee (IECs) and Health Authorities.

The changes described in this amended protocol require IRB/IEC approval prior to implementation.

The changes herein affect the Informed Consent. Sites are required to update and submit for approval a revised Informed Consent that takes into account the changes described in this protocol amendment.

Amendment 4 (22-Nov2017)

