Grade 2 (>160 - 250 mg/dL) [> 8.9 - 13.9 mmol/L]	
Maintain dose level and remind patient on lifestyle changes*, exclude confounding factors like e.g. urinary tract infection, consider consultation with a diabetologist and start oral-antidiabetic treatment, e.g. metformin 500 mg bid with breakfast and dinner. If no GI intolerance, increase to 500 mg with breakfast, 1000 mg with dinner. If tolerated, 1000 mg bid with breakfast and dinner. If not tolerated, reduce to prior tolerated dose. Titrate to the maximum tolerated dose over a period of 3 weeks. A second oral hypoglycemic agent may be initiated if needed.
 
If FPG is still rising on maximum tolerated dose of metformin or persistently >160mg/dl (>8.9 mmol/L, add an SGLT2 inhibitor if available, e.g. empagliflozin up to 25 mg (max. dose). Alternatively, an insulin-sensitizer, e.g. pioglitazone 30 mg (max. dose) can be added.
 
Monitor FPG as clinically indicated and at least weekly until FPG resolves to ≤ Grade 1
 
 ● If FPG does not resolve to ≤ Grade 1 within 21 days after institution of appropriate anti-diabetic treatment, reduce alpelisib/placebo by 1 dose level ● Continue with anti-diabetic treatment and check FPG at least weekly for 8 weeks, then continue checking at least every 2 weeks, alert treating physician if FPG>250mg/dl

Dose Modifications for alpelisib/placebo as specified below. Fulvestrant may be continued while alpelisib/placebo dose is being held, at the investigators discretion, and as specified in Section 6.3.1	
Worst toxicity -CTCAE Grade (value)	Dose Modifications for alpelisib/placebo

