Grade 3 (FPG > 250 - 500 mg/dL) [> 13.9 - 27.8 mmol/L]	
Omit alpelisib/placebo and confirm fasting status of the assessment. If non-fasting, re-check within 24 hours.
 
Regardless of fasting status, consider IV fluids if symptoms of hyperglycemia or signs of volume depletion.
 
Exclude confounding factors like e.g. urinary tract infection and consider consultation with a diabetologist.
 
Administer intravenous hydration and intervention for electrolyte/ketoacidosis/hyperosmolar disturbances as clinically appropriate. Start metformin and titrate as outlined for Grade 2, add insulin sensitizers (i.e. pioglitazone) or a SGLT2 inhibitor, if available, as outlined for Grade 2. Insulin may be used for 1-2 days until hyperglycemia resolves, however this may not be necessary in the majority of alpelisib-induced hyperglycemia given the short half-life of alpelisib.
 
Monitor FPG as clinically indicated and at least twice weekly until FPG resolves to \leq Grade 1.
 
 • If FPG resolves to \leq 160 mg/dL within 3-5 days, while off study treatment and on metformin, re-start alpelisib/placebo and reduce 1 dose level, continue with anti-diabetic treatment..A second and third oral hypoglycemic agent may be initiated concomitantly, if needed, in consultation with a diabetologist. Check FPG at least weekly for 8 weeks, then continue checking at least every 2 weeks, alert treating physician if FPG>250mg/dl • If FPG does not resolve to \leq 160 mg/dL within 3-5 days while off study treatment and on metformin, consult a diabetologist for management of diabetes is strongly recommended. • If FPG does not resolve to \leq 160 mg/dL within 21 days after institution of appropriate anti-diabetic treatment in cooperation with diabetologist and exclusion of confounding factors e.g. urinary tract infection, permanently discontinue patient from alpelisib/placebo treatment.

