Grade 4 (FPG > 500 mg/dL) [≥ 27.8 mmol/L]	
Omit alpelisib/placebo, confirm fasting status of the assessment. If non-fasting, re-check within 24 hours.
 
 • Regardless of fasting status, consider IV fluids. Exclude confounding factors like e.g. urinary tract infection. • Should consult with diabetologist, initiate or intensify medication with appropriate anti-diabetic treatment (see Grade 3), re-check within 24 hours. • If grade improves then follow specific grade recommendations • If FPG is confirmed at Grade 4 and confounding factors could be excluded, permanently discontinue patient from alpelisib/placebo.

Dose Modifications for alpelisib/placebo as specified below. Fulvestrant may be continued while alpelisib/placebo dose is being held, at the investigators discretion, and as specified in Section 6.3.1	
Worst toxicity -CTCAE Grade (value)	Dose Modifications for alpelisib/placebo
A diabetologist consultation should always be considered. For all grades : instruct patient to follow dietary guidelines according to local and/or institutional standards for management of diabetes mellitus (such as those provided by the American Diabetes Association) during the study, e.g. controlled carbohydrate intake, high fiber, low processed food intake; three macronutrient balanced meals and 2 small snacks rather than one large meal.	
* specific recommendations please see Section 6.3.2.1.3 .	
Thrombocytopenia	
Grade 1 (PLT < LLN - $75 \times 10^9/L$)	Maintain dose level
Grade 2 (PLT < $75 - 50 \times 10^9/L$)	
Grade 3 (PLT < $50-25 \times 10^9/L$)	Omit dose until resolved to \leq Grade 1, then: 
 • If resolved in \leq 7 days, then maintain dose level • If resolved in $>$ 7 days, then \downarrow 1 dose level
Grade 4 (PLT < $25 \times 10^9/L$)	Omit dose until resolved to \leq Grade 1, then \downarrow 1 dose level
Investigations (Renal)	
Serum creatinine	
< 2 x ULN	Maintain dose level
2 – 3 x ULN	Omit dose until resolved to \leq grade 1, then: 
 • If resolved in \leq 7 days, then maintain dose level • If resolved in $>$ 7 days, then \downarrow 1 dose level
Grade 3 (> 3.0 – 6.0 x ULN)	Permanently discontinue patient from alpelisib/placebo
Grade 4 (> 6.0 x ULN)	Permanently discontinue patient from alpelisib/placebo
Investigations (Hepatic)	
Isolated total Bilirubin elevation	

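### The rule to stop all glucose-lowering drugs when alpelisib stops has no visible exception for uncontrolled glucose or pre-existing type 2 diabetes: a minor safety wording correction

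*Protocol*

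**What the plan says.** Protocol 6.3.2.1.3, on alpelisib-induced hyperglycaemia, ends its management paragraph with the instruction "Due to the short half-life of alpelisib, all glucose lowering medications should be discontinued when alpelisib is stopped". The Amendment 5 list of changes describes the revision to this section as "Update on guidance for glucose lowering medications after discontinuation of alpelisib".

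The same section also says "Local protocols per standard clinical practice may be followed for monitoring and managing hyperglycemia", and it expects diabetic patients in the trial: "those with an established diagnosis of type 2 diabetes mellitus should be monitored carefully". Exclusion criterion 12 (Section 5.3) removes type I diabetes and type II that is not controlled, so controlled type II can enter.

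Table 6-3 (Section 6.3.1.2) has two routes by which hyperglycaemia itself ends alpelisib/placebo for good:

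- **Grade 3.** The drug is withheld and anti-diabetic treatment given. It is permanently stopped if FPG has not come down to 160 mg/dL or less "within 21 days after institution of appropriate anti-diabetic treatment in cooperation with diabetologist and exclusion of confounding factors".
- **Grade 4 (FPG above 500 mg/dL).** The site is told to "initiate or intensify medication with appropriate anti-diabetic treatment (see Grade 3), re-check within 24 hours". Then: "If FPG is confirmed at Grade 4 and confounding factors could be excluded, permanently discontinue patient from alpelisib/placebo".

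The table does not say what happens to the anti-diabetic drugs once alpelisib/placebo has been permanently stopped.

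**The concern.** The instruction applies to *all* glucose-lowering drugs and carries no condition. It makes sense for the patient it seems to have in mind: someone whose glucose rose on alpelisib and will fall once the drug clears, so that continued anti-diabetic treatment risks hypoglycaemia. It does not suit every patient to whom the words apply. Followed literally, it removes treatment from a patient who came off alpelisib/placebo because glucose could not be controlled, and from a patient with type 2 diabetes that was there before the trial.

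What is at stake is the care of individual patients after discontinuation. No endpoint, sample size or error rate is involved.

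**Working it through.** No design figure is involved. The check sets the rule's stated reason against the patients it covers.

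**1. What *stopped* means.** The sentence does not separate interruption from permanent discontinuation. The Amendment 5 change list refers to the period after discontinuation, so I read it as permanent discontinuation. On that reading it does not clash with Table 6-3's use of metformin while alpelisib is temporarily withheld at Grade 3.

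**2. The half-life reason in numbers.** Input: half-life 8 to 9 h (Protocol 1.2.2.3). Assumption: first-order elimination, so the fraction left after *t* hours is 2^(−t / half-life).

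- At 24 h (the Grade 4 re-check): 2^(−24/8) = 12.5%; 2^(−24/9) = 15.7%.
- At 72 h: 2^(−72/8) = 0.20%; 2^(−72/9) = 0.39%.
- At 21 days (504 h): 504/9 = 56 half-lives; 504/8 = 63 half-lives.

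**3. Applied to each group.**

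- *Unresolved Grade 3, off drug for the full 21 days.* After 56 to 63 half-lives no meaningful drug is left. If FPG is still above 160 mg/dL, clearance of alpelisib gives no reason to expect it to fall, and the stated reason does not support withdrawing treatment.
- *Unresolved Grade 3, off drug for less time.* The 21 days run from the start of anti-diabetic treatment, which can begin while the patient is still on drug. At Grade 2, for example, the table keeps the dose and says to "consider consultation with a diabetologist and start oral-antidiabetic treatment, e.g. metformin 500 mg bid with breakfast and dinner". The 56 to 63 figure does not apply to such a patient.
- *Confirmed Grade 4.* At the 24-hour re-check 12.5% to 15.7% of drug remains, so glucose may yet fall and the reason is not refuted. The sentence nevertheless sets no FPG condition for withdrawal.
- *Controlled type 2 diabetes before the trial.* The half-life of alpelisib has no bearing on disease that predates it. This gap arises at any permanent stop, including one for progression.

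**4. How many patients.** The documents give no rate for these subsets. Grade 3/4 hyperglycaemia at 300 mg was 0 of 9 with fulvestrant (Table 1-2), and Grade 3 was 12% at 300 mg with letrozole (Section 1.2.3.2); neither isolates them. Enrolment closed on 21 July 2017 and Amendment 5 is dated 11 February 2020, 30.7 months later (935 days / 30.4375). Section 6.3.2.1.3 puts typical onset in the first month, so few new cases would arise under the current text. The entry limits of FPG 140 mg/dL and HbA1c 6.4% narrow the diabetic group.

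**5. A separate inconsistency, diarrhoea.** Under a heading that pools Grades 3 and 4, Appendix 4 says to delay the next cycle by one or two weeks and continue once diarrhoea has resolved. Table 6-3 discontinues at Grade 4 and drops one dose level at Grade 3, and Section 6.3.1.2 makes the table's discontinuations mandatory. The table therefore prevails. It also points sites to Appendix 4, where the line does not carry the same limits.

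**The case against.** The best defence is context. The sentence sits under a heading about alpelisib-induced hyperglycaemia, follows a warning about hypoglycaemia, and gives alpelisib's half-life as its reason. A sensible investigator would take it to mean drugs started for that condition. It is also only a *should*, and other text points the same way:

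- Section 6.3.1.2 lets clinical judgment guide each patient's management.
- The Grade 3 row strongly recommends a diabetologist if FPG has not resolved in 3 to 5 days off drug, and it makes the 21-day stop conditional on treatment given in cooperation with one.
- Section 6.3.2 requires follow-up of the event to resolution or stabilization.
- Section 8.1.1 asks for appropriate treatment of every adverse event.
- Section 6.3.2.1.3 itself allows local practice.

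This stands as mitigation and is why the point is minor. None of these clauses is an exception to the sentence, and the heading and reason suggest the intent without limiting the word *all*.

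A second defence also stands in part. Concomitant therapy (Section 6.4) and Appendix 1 are redacted, and a rule on baseline anti-diabetic drugs could be there. The claim is therefore limited to the visible text.

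Three stronger readings are tempting and are not supported:

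- *That the rule contradicts Table 6-3.* On the permanent-stop reading it does not. The table is silent on anti-diabetic drugs after permanent discontinuation.
- *That patients entered on anti-diabetic drugs because FPG of 126 to 140 mg/dL is eligible and SAP 3.13.1 classes it as diabetic.* A baseline laboratory category does not show that anyone was being treated. The documents show only that controlled type 2 diabetes is eligible.
- *That the plan lets patients resume after Grade 4 diarrhoea.* The mandatory stop in Table 6-3 settles that.

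**Conclusion.** The concern holds as a minor safety wording correction. The instruction in 6.3.2.1.3 is broader than its stated reason: that reason fails for pre-existing diabetes and for Grade 3 hyperglycaemia unresolved after a full 21 days off drug, and it remains open for Grade 4 at 24 hours. Few patients are likely to be affected, though the documents do not allow a count. Nothing in the trial's size, analysis or conclusions changes.

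The conclusion assumes that *stopped* means permanent discontinuation, that elimination is first-order at the stated half-life, and that the redacted Section 6.4 contains no exception. If it does contain one, a cross-reference from 6.3.2.1.3 would be enough. The diarrhoea line is a residual inconsistency and adds no weight to the glucose point.

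**What to change.** By amendment or site letter, replace the sentence in 6.3.2.1.3 with wording to this effect: after permanent discontinuation of alpelisib/placebo, glucose-lowering drugs that were started for alpelisib-induced hyperglycaemia are reduced and withdrawn according to FPG as it resolves; anti-diabetic therapy in use before the trial is not withdrawn by this rule.

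As a tidy-up in the same document, limit the delay-and-continue line in Appendix 4 to Grade 3, with the one-level dose reduction from Table 6-3, and state that alpelisib/placebo is discontinued at Grade 4.

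The cost is one or two sentences in each place. There is no change to sample size, data collection or analysis.

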6.3.2.1.5 Follow up on potential drug-induced liver injury (DILI) cases

Patients with transaminase increase combined with total bilirubin (TBIL) increase may be indicative of potential DILI, and should be considered as clinically important events.

In general, any increase of serum aminotransferases to $> 3 \times$ ULN should be followed by repeat testing within 48 to 72 hours.

If total bilirubin is elevated $> 2 \times$ ULN, fractionation into direct and indirect bilirubin is required. The threshold for potential DILI may depend on the patient's baseline AST/ALT and TBIL value; patients meeting any of the following criteria will require further follow-up as outlined below:

- For patients with normal ALT and AST and TBIL value at baseline: AST or ALT $> 3.0 \times$ ULN combined with TBIL $> 2.0 \times$ ULN
- For patients with elevated AST or ALT or TBIL value at baseline: [AST or ALT $> 2 \times$ baseline AND $> 3.0 \times$ ULN] OR [AST or ALT $> 8.0 \times$ ULN], combined with [TBIL $> 2 \times$ baseline AND $> 2.0 \times$ ULN]

Medical review needs to ensure that liver test elevations are not caused by cholestasis, defined as ALP elevation $> 2.0 \times$ ULN with R value < 2 in patients without bone metastasis, or elevation of ALP liver fraction in patients with bone metastasis.

Note: (The R value is calculated by dividing the ALT by the ALP, using multiples of the ULN for both values. It denotes the relative pattern of ALT and/or ALP elevation is due to cholestatic (R ≤ 2), hepatocellular (R ≥ 5), or mixed (R > 2 and < 5) liver injury).

In the absence of cholestasis, these patients should be immediately discontinued from study drug treatment, and repeat LFT testing as soon as possible, preferably within 48 hours from the awareness of the abnormal results. The evaluation should include laboratory tests, detailed history, physical assessment and the possibility of liver metastasis or new liver lesions, obstructions/compressions, etc.

Upon presentation:

1. Obtain PK sample, as close as possible to last dose of study drug, to determine exposure to study drug and metabolites
2. Perform comprehensive medical history including cardiac disease, blood transfusions, i.v. drug abuse, travel, work, alcohol intake, and full clinical examination for evidence of acute or chronic liver disease, cardiac disease and infection etc
3. History of concomitant drug use (including nonprescription medications and herbal and dietary supplement preparations), alcohol use, recreational drug use, special diets, and chemicals exposed to within one month of the onset of the liver injury 4. Exclude other causes of liver disease. Further testing for acute hepatitis A, B, C or E infection and liver imaging (e.g. biliary tract) may be warranted

Obtain PK sample, as close as possible to last dose of study drug, to determine exposure to study drug and metabolites

Patient monitoring:

- Repeat liver chemistry tests within 48-72 hours
- Retest frequency can decrease to weekly or less if abnormalities stabilize, drug has been discontinued, and the patient is asymptomatic.

As DILI is essentially a diagnosis of exclusion, other causes of abnormal liver tests should be considered and their role clarified before the diagnosis of DILI is confirmed (see [Table 6-4](#)). Liver biopsy has limited value in the diagnosis of DILI as histopathological findings in DILI can resemble many other liver conditions. However, biopsy can be useful to establish an alternative diagnosis especially if other tests are inconclusive.

If DILI confirmed: permanently discontinue.

If DILI unlikely - interrupt treatment. Treat identified cause according to institutional guidelines. If resolved, reduce by one dose level. Re-administration of study treatment should be considered only if the investigator assesses benefit to outweigh the risk. Any decision regarding re-administration of study drug/s and dose regimen should be discussed with the Novartis medical safety team.

Table 6-4 Alternative causes of liver disease

Disease	Assessment
Hepatitis A, B, C, E	IgM anti-HAV; HBsAg, IgM anti-HBc, HBV DNA; anti-HCV, HCV RNA, IgM & IgG anti-HEV, HEV RNA
CMV, HSV, EBV infection	IgM & IgG anti-CMV, IgM & IgG anti-HSV; IgM & IgG anti-EBV
Autoimmune hepatitis	ANA & ASMA titers, total IgM, IgG, IgE, IgA
Alcoholic hepatitis	Ethanol history, gammaGT, MCV, CD-transferrin
Nonalcoholic steatohepatitis	Ultrasound or MRI
Hypoxic/ischemic hepatopathy	Medical history: acute or chronic CHF, hypotension, hypoxia, hepatic venous occlusion. Ultrasound or MRI.
Biliary tract disease	Ultrasound or MRI, ERCP as appropriate.
Wilson disease	Caeruloplasmin
Hemochromatosis	Ferritin, transferrin
Alpha-1-antitrypsin deficiency	Alpha-1-antitrypsin

Following appropriate causality assessments, as outlined above, the causality of the drug is estimated as "probable" i.e. > 50% likely, if it appears greater than all other causes combined. The term "drug-induced" indicates probably caused by the drug, not by something else, and only such a case can be considered a DILI case and should be reported as an SAE.

All cases confirmed on repeat testing meeting the laboratory criteria defined above, with no other alternative cause for LFT abnormalities identified should be considered as "medically significant", thus, met the definition of SAE ([Section 8.2.1](#)) and reported as SAE using the term "potential drug-induced liver injury". All events should be followed up with the outcome clearly documented

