8.1 Adverse events

8.1.1 Definitions and reporting

An adverse event is defined as the appearance of (or worsening of any pre-existing) undesirable sign(s), symptom(s), or medical condition(s) that occur after patient's signed informed consent has been obtained.

Abnormal laboratory values or test results occurring after informed consent constitute adverse events only if they induce clinical signs or symptoms, are considered clinically significant, require therapy (e.g. hematologic abnormality that requires transfusion or hematological stem cell support), or require changes in study medication(s).

Adverse events that begin or worsen after informed consent should be recorded in the adverse events CRF. Conditions that were already present at the time of informed consent should be recorded in the Medical History page of the patient's CRF. Adverse event monitoring should be continued for at least 30 days following the last dose of study treatment. Adverse events (including lab abnormalities that constitute AEs) should be described using a diagnosis whenever possible, rather than individual underlying signs and symptoms. When a clear diagnosis cannot be identified, each sign or symptom should be reported as a separate Adverse Event.

Adverse events will be assessed according to the Common Terminology Criteria for Adverse Events (CTCAE) version 4.03.

If CTCAE grading does not exist for an adverse event, the severity of mild, moderate, severe, and life-threatening, corresponding to Grades 1 - 4, will be used. CTCAE Grade 5 (death) will not be used in this study; rather, information about deaths will be collected through a Death form.

The occurrence of adverse events should be sought by non-directive questioning of the patient (subject) during the screening process after signing informed consent and at each visit during the study. Adverse events also may be detected when they are volunteered by the patient (subject) during the screening process or between visits, or through physical examination, laboratory test, or other assessments. As far as possible, each adverse event should be evaluated to determine:

1. The severity grade (CTCAE Grade 1-4)
2. Its duration (Start and end dates)
3. Its relationship to the study treatment (Reasonable possibility that adverse event is related: No, Yes)
4. Action taken with respect to study or investigational treatment (none, dose adjusted, temporarily interrupted, permanently discontinued, unknown, not applicable)

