8.2.2 Reporting

To ensure patient safety, every Serious Adverse Event, regardless of suspected causality, occurring after the patient has provided main informed consent and until at least 30 days after the patient has stopped study treatment must be reported to Novartis within 24 hours of learning of its occurrence.

Any additional information for the SAE including complications, progression of the initial SAE, and recurrent episodes must be reported as follow-up to the original episode within 24 hours of the investigator receiving the follow-up information. An SAE occurring at a different time interval or otherwise considered completely unrelated to a previously reported one should be reported separately as a new event.

Any Serious Adverse Events experienced after this 30 days period should only be reported to Novartis if the investigator suspects a causal relationship to the study treatment.

Information about all Serious Adverse Events is collected and recorded on the Serious Adverse Event Report Form; all applicable sections of the form must be completed in order to provide a clinically thorough report. The investigator must assess and record the relationship of each Serious Adverse Event to each specific study treatment (if there is more than one study treatment), complete the Serious Adverse Event Report Form in English, and submit the completed form within 24 hours to Novartis. Detailed instructions regarding the SAE submission process and requirements for signatures are to be found in the investigator folder provided to each site. Detailed instructions regarding the SAE submission process and requirements for signatures are to be found in the investigator folder provided to each site

Follow-up information is submitted in the same way as the original SAE Report. Follow-up information is submitted in the same way as the original SAE Report. Each re-occurrence, complication, or progression of the original event should be reported as a follow-up to that event regardless of when it occurs. The follow-up information should describe whether the event has resolved or continues, if and how it was treated, whether the blind was broken or not, and whether the patient continued or withdrew from study participation.

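### The liver-injury section gives two different causality conditions for reporting a case as an SAE, neither matches the general SAE rules, and it does not say when the 24-hour clock starts

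*Protocol*

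**What the plan says.** Protocol Section 6.3.2.1.5 first defines laboratory criteria. With normal baseline values these are ALT or AST above 3 x ULN combined with total bilirubin above 2 x ULN; adapted thresholds apply when baseline values are raised. A medical review for cholestasis, repeat testing and a search for other causes (Table 6-4) follow. Two closing paragraphs then deal with reporting.

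- Paragraph 1 applies after the causality assessment: "the causality of the drug is estimated as 'probable' i.e. > 50% likely, if it appears greater than all other causes combined". It adds that "only such a case can be considered a DILI case and should be reported as an SAE".
- Paragraph 2 covers "All cases confirmed on repeat testing meeting the laboratory criteria defined above, with no other alternative cause for LFT abnormalities identified". These are to be regarded as medically significant, as meeting the SAE definition in 8.2.1, and as reportable under the term potential drug-induced liver injury.

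The general rules are in Section 8. The SAE definition in 8.2.1 has no causality element. Section 8.2.2 covers "every Serious Adverse Event, regardless of suspected causality", from main consent until at least 30 days after treatment stops, and each such event "must be reported to Novartis within 24 hours of learning of its occurrence". Suspected causality becomes a condition only after that period. Section 8.1.2.1 adds that a Grade 3 or 4 laboratory value is not automatically an SAE; it must meet the seriousness definition and/or be judged serious by the investigator.

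**The concern.** Seriousness and causality are separate judgements in Section 8. Section 6.3.2.1.5 links them, and does so in two different ways, so a site can find opposite instructions for the same patient in consecutive paragraphs.

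This matters most for cases defined by laboratory values alone. Table 6-3 sends combined transaminase and bilirubin elevations to this section, and this section is the text that classes them as medically significant. If its reporting clause is unclear, 8.1.2.1 leaves the decision largely to investigator discretion.

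Competing explanations are foreseeable in this population. Patients with liver metastases may enter with ALT and AST up to 5 x ULN (inclusion criterion 12), and Section 6.3.2.1.5 itself asks the site to consider liver metastasis. Under a test of greater than all other causes combined, the drug can be the single most likely cause and still not qualify.

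At stake are the individual SAE report, any expedited report that depends on it (8.2.2), and the SAE tables by arm (protocol 10.5.3.2; SAP 3.9.1.4).

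**Working it through.** No sample size, alpha or event count is involved, and the plan gives no figure to reproduce. The check sets the reporting rules side by side.

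**Conditions for reporting.** The cases below meet the laboratory criteria on repeat testing, within 30 days of the last dose, with no fatal, life-threatening or hospitalization element.

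| Case | 6.3.2.1.5, paragraph 1 | 6.3.2.1.5, paragraph 2 | 8.2.1 and 8.2.2 |
|---|---|---|---|
| No alternative cause found; drug judged above 50% | Report | Report | Report if medically significant |
| No alternative cause found; drug not judged above 50% | Do not report | Report | Report if medically significant; causality plays no part |
| Contributing alternative cause found; drug judged above 50% | Report | Not covered | Same |
| Alternative cause found; drug not judged above 50% | Do not report | Not covered | Same |

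The two paragraphs agree that a report is due only in the first row. They disagree in the second and third. In the fourth, neither calls for a report, although 8.2.2 does not let causality decide. Paragraph 2 is therefore not a clean statement of the general rule either: its condition that no other cause be identified is also a causality condition.

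**Timing.** Inputs: 24 hours from learning of the event (8.2.2); repeat liver tests within 48 to 72 hours, or preferably within 48 hours once the criteria are met (6.3.2.1.5). Suppose that the clock starts at the first qualifying result and that the site waits for the repeat test:

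- repeat at 48 hours: 48 − 24 = 24 hours past the limit;
- repeat at 72 hours: 72 − 24 = 48 hours past the limit.

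Serology and imaging would add to this. If the clock starts only at confirmation, the repeat test causes no overrun. Section 6.3.2.1.5 does not say which applies.

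**What the analysis still sees.** SAP 3.9.2.2 counts patients with ALT or AST above 3 x ULN and total bilirubin above 2 x ULN, without a time window and without a causality judgement. Both sets of criteria in 6.3.2.1.5 require at least these values: the raised-baseline alternative of above 8 x ULN exceeds 3 x ULN, and bilirubin must exceed 2 x ULN in either set. Every on-treatment case that meets the protocol criteria therefore falls in this SAP row.

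**The case against.** The strongest reply is that 8.2.2 governs events that are already SAEs. It does not make a laboratory combination serious, and 8.1.2.1 says that severity grade alone does not. On this view, 6.3.2.1.5 adds a route to seriousness and takes nothing away from 8.2.1. The word only can also be read as restricting the DILI label, with paragraph 2 as the working rule under a different term. The two paragraphs will often agree, because a confirmed case with no other cause found will usually be judged probable.

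Much of this stands. A reader might infer that a liver case with a competing explanation is not an SAE at all. That is not supported: fatal, life-threatening or hospitalized cases remain SAEs under 8.2.1, apart from documented progression, which 8.1.1 exempts. A reader might also see a conflict with the reasonable-possibility item in 8.1.1. That item records the relationship for each adverse event, whereas the 50% standard serves the DILI diagnosis, so the two can coexist.

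The label-only reading does not remove the problem. The sentence joins the label to SAE reporting, and even on that reading paragraph 2 keeps a causality condition that 8.2.2 does not have.

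**Conclusion.** The inconsistency is real and is in the current text. Laboratory-defined liver cases whose seriousness rests on being medically significant can go unreported under paragraph 1, under paragraph 2, or under both. They can be reported late if sites wait for the work-up. Lateness is conditional: it assumes that the clock starts at the first qualifying result, in which case waiting for the repeat test alone costs up to 24 to 48 hours.

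The consequence is confined to individual and expedited reporting and the SAE tables. Two wider conclusions are tempting but not supported.

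- **That a liver signal would be lost to the analysis.** The SAP laboratory tables show these patients by arm whatever the cause, and the DMC reviews unblinded safety data about every six months (protocol 8.6).
- **That under-reporting differs between arms because investigators can guess the treatment.** The documents neither state nor quantify this, and the point does not depend on it.

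The number of affected cases is not given and is probably small. The correction is still worth making, because each is a key liver case and the change is cheap.

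**What to change.** In Section 6.3.2.1.5:

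1. Delete the SAE clause from the end of the sentence in paragraph 1, so that the 50% standard applies only to labelling a case as confirmed DILI.
2. Reconcile paragraph 2 with 8.2.2. A case that meets the section's laboratory criteria should be reported as potential drug-induced liver injury without waiting for the causality work-up. Two limits should be written in: the section's existing cholestasis review comes first, and documented progression stays exempt under 8.1.1. Without them, a rule to report every laboratory case whatever its cause would conflict with both provisions.
3. State which result starts the 24-hour clock.
4. State that the repeat test, alternative causes and final causality are submitted as follow-up information, a route that 8.2.2 already provides.

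The cost is protocol wording and a site memo. The downside is a few additional SAE reports that later prove to have another cause. No dosing or treatment rule changes.
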